7.4 Handling of missing or partial Prior/Concomitant Medication Dates

Missing or partial medication start date:

- a. If only Day is missing, the first day of the month will be assumed.
- b. If Day and Month are both missing, the first day of the year will be assumed.
- c. If Day, Month and Year are all missing, the day before the first dose date will be assumed.

Missing or partial medication stop date:

- a. If only Day is missing, the last day of the month will be assumed.
- b. If Day and Month are both missing, the last day of the year will be assumed.
- c. If Day, Month and year are all missing, ‘ongoing status to stop date will be assigned.

7.4 Multiple Comparisons and Multiplicity

No multiple comparison or multiplicity adjustment will be done based on the objective of the study.

7.5 Adjustments for covariates

Not applicable

7.6 Multicenter Studies

This study will be conducted in up to 3 sites in United States of America.

7.7 Examination of Subgroups

No subgroup analyses are planned.

7.8 Coding dictionaries

Medical history, concomitant procedures and AEs will be coded using the Medical Dictionary for Regulatory Activities (MedDRA) Version 24.0 or higher. Medications will be coded using the World Health Organization Drug Dictionary (WHO Global B3 format - March 2021 or higher).

7.8 Analysis Sets

7.8.1 Safety Population

All participants who received any amount of study drug (GBT021601).

7.8.2 Pharmacokinetic Population

All participants who received at least 1 dose of GBT021601 and have at least 1 plasma or whole blood concentration data point.

7.9 Participant Accountability

Summaries of analysis populations and subject disposition will be presented by overall and will contain the following information:

- Number and percent of subjects received any dose (Safety Population)
- Number of subjects who completed Single dose period
- Number of subjects who completed Multiple ascending-dose period
- Number and percent of subjects who completed the treatment
- Number and percent of subjects who discontinued the treatment and reason for early discontinuation of the treatment
- Number and percent of subjects who completed the study
- Number and percent of subjects who discontinued early and reason for early discontinuation
- Number and percent of participants in the PK full and PK evaluable population.

Percentage will be based on the number of safety population. Participant disposition will be presented in listing for all safety subjects.

7.10 Protocol Deviations

Major protocol deviations will be identified prior to database lock for any intentional or unintentional change, or noncompliance with the approved protocol procedures or requirements. All protocol deviations will be listed using safety population.

7.11 Participant Demographics and Baseline Characteristics

Participant demographics and baseline characteristics will be listed and summarized descriptively for all participants by overall. The summary will include the participants' age at informed consent (in years), gender, race, ethnicity, weight (in kg), height (in cm), and Body Mass Index (in kg/m²) using safety population.

7.12 Baseline Sickle Cell Disease

Number of Vaso-Occlusive Crisis (VOC) including the number of VOCs requiring hospitalization and the number of blood transfusion during the previous 12 months will be summarized categorically.

Additional summaries including the number and percentage of subjects who currently use hydroxyurea, who have each genotype (HbSS or HbS β⁰ Thalassemia) and who experienced a sickle cell complication prior to study enrolment will be presented. Baseline lab values including Hb and reticulocyte count will be summarized using descriptive statistics.

7.13 Hemoglobin Response

Hemoglobin response, defined as an increase in Hb > 1 g/dL, will be listed and summarized descriptively at each postdose visit. Subjects who discontinue early or do not have a postdose visit, are not included in the analysis for Hb response. No missing data imputation or adjustment for transfusion will be performed for this endpoint.

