3. INTRODUCTION AND BACKGROUND

3.1. Introduction

Global Blood Therapeutics, Inc. (GBT; the Sponsor) intends to develop GBT021601, a sickle hemoglobin (HbS) polymerization inhibitor for the treatment of sickle cell disease (SCD).

Sickle cell disease is an inherited disorder caused by a point mutation in the β -globin gene leading to formation of HbS. A primary and obligatory event in the molecular pathogenesis of SCD is the polymerization of intracellular HbS following deoxygenation in the microvasculature. HbS polymerization leads to decreased red blood cells (RBC) deformability, morphologic sickling of RBCs, decreased RBC survival, and microvascular obstruction (Bunn, 1997).

Clinically, SCD is a devastating and debilitating disease marked by the pathophysiologic features of hemolytic anemia, vaso-occlusion, and progressive end-organ damage. Despite current standards of care, including hydroxyurea (HU), blood transfusion, and supportive care with analgesia, patients with SCD continue to suffer serious morbidity and premature mortality.

A drug that inhibits HbS polymerization in all RBCs has the potential to provide superior efficacy to available treatments. GBT021601 is an HbS polymerization inhibitor being developed by GBT for the treatment of SCD. GBT021601 increases hemoglobin-oxygen (Hb-O₂) affinity and stabilizes hemoglobin (Hb) in the oxy-hemoglobin (oxyHb) state thereby inhibiting polymerization of HbS in RBCs. By addressing this underlying mechanism of SCD, GBT021601 has the potential to be a disease-modifying therapy, leading to improved anemia, reduced hemolysis and the potential to reduce the end-organ damage resulting from chronic hemolytic anemia. Proof of concept for this Hb modification approach has been provided with voxelotor, an orally administered small molecule inhibitor of HbS polymerization.

Voxelotor is an allosteric modifier of Hb-O₂ affinity and following binding to Hb, stabilizes the oxyhemoglobin state (Metcalf, 2017; Oksenberg 2016), thereby inhibiting polymerization of HbS in RBCs and in patients with SCD.

Data from the Phase 3 study of voxelotor in patients with SCD showed a dose-dependent improvement in hemolytic anemia, with an increase in Hb and concomitant decrease in clinical measures of hemolysis (including indirect bilirubin, reticulocytes, and lactate dehydrogenase) (Vichinsky, 2019).

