5.2. Participant Exclusion Criteria

Participants meeting any of the following exclusion criteria will not be eligible for study enrollment:

1. More than 10 vaso-occlusive crises within 12 months of Screening that required a telemedicine, hospital, emergency room, or clinic visit.
2. Female participant who is breastfeeding or pregnant.
3. Receiving regularly scheduled RBC transfusion therapy (also termed chronic, prophylactic, or preventive transfusion) or have received an RBC transfusion for any reason within 60 days of signing the ICF or at any time during the Screening period.
4. Hospitalized for sickle cell crisis or other vaso-occlusive event within 14 days of signing the ICF or within 28 days prior to the start of study treatment (ie, participants with a vaso-occlusive event must wait at least 14 days before signing an ICF and Screening period must be at least 14 days before the start of study treatment).

5. Screening laboratory test of alanine aminotransferase (ALT) $> 4 \times$ upper limit of normal (ULN).
6. Acute illness or clinically significant bacterial, fungal, parasitic, or viral infection which requires therapy, including acute bacterial infection requiring antibiotics within 14 days prior to the start of study drug administration.
7. Participants with positive Screening tests for hepatitis (A, B, or C) or human immunodeficiency virus (HIV) or who are known to have active hepatitis infection or to be HIV positive or hepatitis C antibody positive.
8. Participants with symptomatic coronavirus disease 2019 (COVID-19) infection, temporary exclusion.
9. Estimated glomerular filtration rate (eGFR) $< 50 \text{ mL/min}/1.73 \text{ m}^2$ at the Screening Visit, calculated by the central laboratory, or is on chronic dialysis.
10. History of malignancy within the past 2 years prior to treatment Day 1 requiring chemotherapy and/or radiation (with the exception of local therapy for non-melanoma skin malignancy).
11. History of unstable or deteriorating cardiac or pulmonary disease within 6 months prior to consent including but not limited to the following:
 - a. Unstable angina pectoris or myocardial infarction or elective coronary intervention
 - b. Congestive heart failure requiring hospitalization
 - c. Uncontrolled clinically significant arrhythmias, high grade atrioventricular block (ie, Mobitz II or 3rd degree), pacemaker, or implantable cardioverter-defibrillator.
 - d. Pulmonary hypertension

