25. Consumption of grapefruit and/or grapefruit juice within 14 days prior to Day -1 and is unwilling to abstain from consumption of grapefruit and/or grapefruit juice until the EOS/ET.
26. Any other condition or prior therapy that, in the Investigator's opinion, would confound or interfere with the evaluation of or PK, safety, tolerability, and PD of the study drug, interfere with study compliance, or preclude informed consent.
27. History of severe allergic reaction (including anaphylaxis) to any substance, or previous status asthmaticus.

5.2.1. Additional Exclusion Criteria (Part C):

28. More than 10 VOCs within 10 months of Screening.
29. For Part C of the study recent use of voxelotor is defined as within 10 days prior to the start of GBT021601 treatment.
30. Ongoing or recent use of strong or moderate inducers of CYP3A4/CYP3A5. Recent is defined as within 5 elimination half-lives or 14 days, whichever is longer prior to the start of GBT021601 treatment.
31. Ongoing or recent use of strong or moderate inhibitors of CYP3A4/CYP3A5. Recent is defined as within 5 elimination half-lives prior to the start of GBT021601 treatment.
32. Consumption of Seville oranges within 14 days prior to the start of GBT021601 treatment and is unwilling to abstain from consumption of Seville oranges until the EOS/ET Visit.

33. History of overt stroke including hemorrhagic stroke or transient ischemic attack (TIA) or spinal cord injury, magnetic resonance angiography (MRA)-defined vasculopathy, or magnetic resonance imaging (MRI)/transcranial doppler (TCD)-documented silent cerebral infarcts within 2 years of screening.
34. Ongoing or recent (within 2 years) substance abuse (alcohol).
35. Has received COVID-19 vaccine (first dose, second dose, or booster dose), authorized by regional regulatory authority, within 7 days prior to start of GBT021601 treatment.
36. Has received an exchange transfusion for any reason within 90 days prior to the start of GBT021601 treatment.

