6.5. Concomitant Medications, Procedures, Other Restrictions and Requirements

6.5.1. Concomitant Medications and Procedures

Study participants will be allowed to take other medications as needed with the exception of those described listed in Section [6.5.2](#). All concomitant medications will be documented.

In the interests of participant safety and acceptable standards of medical care the Investigator will be permitted to prescribe treatment(s) at his/her discretion. All treatments must be recorded in the participants' electronic case report form (eCRF) (medication, dose, treatment duration and indication).

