3.7 Concomitant Medications and Procedures

Study participants will be allowed to take other medications as needed as described in protocol. All concomitant medications will be documented.

In the interests of participant safety and acceptable standards of medical care the Investigator will be permitted to prescribe treatment(s) at his/her discretion. All treatments must be recorded in the participants' electronic case report form (eCRF) (medication, dose, treatment duration and indication) procedures along with start and stop date, type and reason for procedures will be captured on eCRF.

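### SAP 7.13 makes no allowance for on-study transfusion, so a donor-cell rise can count as an Hb response and a transfused Day 56 baseline can hide one

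*SAP*

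**What the plan says.** SAP 7.13 gives the endpoint and its rule: "Hemoglobin response, defined as an increase in Hb > 1 g/dL, will be listed and summarized descriptively at each postdose visit". Participants who discontinue early or have no postdose visit are left out. The section then states: "No missing data imputation or adjustment for transfusion will be performed for this endpoint". It sets no window after a transfusion and asks for no flag.

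Other sections bear on whether a transfusion can occur and be identified:

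- **Standard care.** Protocol 3.1 describes the disease burden as persisting "Despite current standards of care, including hydroxyurea (HU), blood transfusion, and supportive care with analgesia". SAP 7.12 adds that "the number of blood transfusion during the previous 12 months will be summarized categorically".
- **Entry.** Protocol 5.2, criterion 3, excludes people on regular transfusion and those who "have received an RBC transfusion for any reason within 60 days of signing the ICF or at any time during the Screening period". For Part C, criterion 36 in 5.2.1 adds: "Has received an exchange transfusion for any reason within 90 days prior to the start of GBT021601 treatment".
- **On study.** Under Protocol 6.5.1, "the Investigator will be permitted to prescribe treatment(s) at his/her discretion". The restriction list in 6.5.2 does not mention transfusion, and 5.4 does not name it as a reason for withdrawal.
- **Baseline.** SAP 7.1 uses the average of the screening and Day -1 values for Part A, and the Day 56 value for both Part B and Part C.
- **Data.** SAP 3.7 says that "procedures along with start and stop date, type and reason for procedures will be captured on eCRF".

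**The concern.** The endpoint is a threshold on the same quantity that a red-cell transfusion is given to raise. If a participant is transfused after baseline and the next scheduled Hb is more than 1 g/dL up, the rule as written counts a response, whatever the study drug did. A transfusion may well be given when a participant is doing badly, so a deterioration could appear in the table as an improvement. There is no control group in which the same event would show.

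The rate is likely to be read as evidence about the drug. Protocol 3.1 cites the same threshold for voxelotor, with a rise above 1 g/dL in more than 50% of patients, as clinically meaningful. Protocol 3.4.2.3 says a dose-ranging study is being planned and that the effect on hematological parameters at the Part C regimen needs to be known.

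The fixed Day 56 baseline opens a second route to error. A transfusion shortly before Day 56 would raise the reference value for all of Parts B and C.

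**Working it through.** The plan states no response rate, power or sample-size calculation, so there is no figure of its own to reproduce. The check is of what the rule does.

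**1. Direction.** Let *t* be the change in Hb without a transfusion and *d* > 0 what the transfusion adds to a measured value.

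- Transfusion after baseline: observed change = *t* + *d*. A false response is counted when *t* ≤ 1 < *t* + *d*.
- Transfusion before the Day 56 baseline, with its effect gone by the later visit: observed change = *t* − *d*. A response is missed when *t* > 1 ≥ *t* − *d*.

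A single transfusion between Day 1 and Day 56 could do both: raise the change in Part A, whose baseline precedes it, and lower the change in Parts B and C.

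**2. Weight of one participant.** The shift is 1/*n*: 1/6 = 16.7 points, 1/5 = 20.0, 1/4 = 25.0. The smaller denominators matter because SAP 7.13 drops early discontinuers.

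**3. Illustration.** Take 6 participants with 4 apparent responders, one of whom is a responder only because of a transfusion. Intervals are exact (Clopper-Pearson) 95%.

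| Handling | Rate | 95% interval |
|---|---|---|
| As written in SAP 7.13 | 4/6 = 66.7% | 22.3 to 95.7 |
| Post-transfusion value classed as non-response | 3/6 = 50.0% | 11.8 to 88.2 |
| Post-transfusion value set aside | 3/5 = 60.0% | 14.7 to 94.7 |

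**4. How many visits.** The documents do not say how long a transfusion affects Hb. If the 60 days of criterion 3 are borrowed as a yardstick:

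- Part B treatment lasts 112 − 56 = 56 days, and Part C treatment 42 days. Both are shorter than 60.
- A transfusion on Day 70 gives a window to Day 130, beyond the last Part B treatment visit on Day 112.
- A transfusion on Part C Day 7 gives a window to Day 67, beyond the Week 6 visit on Day 42.

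On that yardstick, one early transfusion could touch every later treatment visit in its Part.

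**5. Chance of at least one transfusion.** The on-study rate is not given, so the per-participant risk *p* is an assumption. With 6 independent participants the chance is 1 − (1 − *p*)^6.

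| Assumed *p* | 2% | 5% | 10% | 20% | 30% |
|---|---|---|---|---|---|
| At least one of 6 | 11.4% | 26.5% | 46.9% | 73.8% | 88.2% |

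This is the chance that a transfusion occurs, not that a response is misclassified.

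**The case against.** Much can be said for the plan. Protocol section 11 makes all analyses descriptive, SAP 3.9 calls efficacy evaluation not applicable, and Hb response is not among the visible objectives, so no test or error rate is affected. The rule is disclosed, responses are listed by participant, and procedures are recorded with dates. With six participants a transfused case could be traced. The visible SAP text does not show the full list of outputs, so a procedures listing may exist. All of this lowers the weight of the point, but none of it corrects the summary rate, and no visible section links the two sources.

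Four stronger readings are tempting, and the documents do not support them:

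- *The bias always favours the drug.* The Day 56 baseline can work against it, and a transfused participant who discontinues early is dropped, not counted as a responder.
- *Transfusion is to be expected on study.* Regularly and recently transfused people are excluded, entry Hb must be stable, and no frequency is given. Transfusion is plausible and unrestricted, no more.
- *The protocol itself holds Hb invalid for 60 or 90 days after transfusion.* Those are entry criteria with no stated rationale. Criterion 3 runs back from consent, and neither is described as a washout for Hb.
- *Affected values should come out of every Hb and hemolysis summary.* These are safety laboratory data and safety is the primary objective. Removing them could hide most of a participant's values at the time they matter most. The sentence in SAP 7.13 is also limited to this one endpoint.

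**Conclusion.** The point holds as a flaw in a stated rule. Followed literally, SAP 7.13 can tabulate a transfusion-produced rise as an Hb response, and the Day 56 baseline can conceal a real one. The effect is up to 16.7 points on a visit's rate at *n* = 6. That maximum requires that the transfusion alone carries the participant across the 1 g/dL line, in either direction. The documents give no figure for the Hb rise after a transfusion, so that it exceeds 1 g/dL is an assumption. The probability of the problem arising cannot be stated. The point is worth correcting before the analysis because the table is small and uncontrolled, but it does not touch the primary safety objective or any formal inference.

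**What to change.** Replace the last sentence of SAP 7.13 with a rule along these lines, for the Hb response summary only:

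- Hb values within a pre-stated window after a red-cell transfusion are classed as non-response at that visit and flagged in the listing. The entry criteria offer candidate lengths: 60 days, or 90 days after exchange transfusion. The SAP should say that these are borrowed.
- If the Day 56 baseline falls in such a window, the last pre-transfusion value is the baseline for this endpoint.
- The unadjusted rate is shown beside the adjusted one as a sensitivity display.
- The number of participants transfused is reported for each Part.

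Keep the safety laboratory summaries as observed, with the flag shown. Run the concentration-response pairs for Hb and hemolysis measures (a secondary objective in Protocol 4.2 and SAP 2.1.2) with and without flagged values. Nothing here changes who may be transfused.

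The cost is SAP wording and one flag derived from procedure data that SAP 3.7 already places on the eCRF. The downside is a possibly lower response rate: with a 60-day window, a participant transfused early in a Part would be a non-responder at every later treatment visit of that Part, even if the drug had worked. The unadjusted display is there for that reason.

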7.14 Medical and Surgical History

The medical and surgical history data will be coded using the Medical Dictionary for Regulatory Activities (MedDRA, Version 24.0 or higher) and will be listed using safety population.

7.15 Measurements of Treatment Compliance

Individual participant listing will be provided for eCRF collected exposure data using safety population.

7.16 Pharmacokinetic Analysis

The PK population will be used for all concentration listings and individual figures. Plasma, RBC (if applicable) and whole blood GBT021601 concentrations will be listed and summarized for each visit/ time point for single dose including n, nBLQ, mean, SD, geometric mean, coefficient of variation (CV), median, minimum and maximum.

The drug concentrations will be presented in graphical formats (linear and semi-log scales) as mean and individual profiles. Overlay of individual RBC, plasma and whole blood GBT021601 concentration profiles over time will be provided.

All plasma, RBC (if applicable) and whole blood GBT021601 PK parameters for single dose will be listed for PK population. Summary statistics (n, mean, SD, geometric mean, median, minimum, maximum, and CV) will be calculated for the plasma, RBC and whole blood GBT021601 PK parameters. For t_{max}, only n, minimum, median and maximum will be reported.

7.17 Safety Analyses

All Safety analysis will be presented using the Safety population.

All safety data will be summarized by Part A (SAD), Part B (MAD) and Part C (extended treatment period) or overall (as applicable), and visit/ time point. No statistical tests will be performed.

7.17.1 Adverse Events

All AE summaries will include treatment emergent AEs and will be presented for SCD related and SCD non-related separately.

SCD related AEs include:

SCD-related AEs comprise the following PTs: sickle cell anemia with crisis, ACS, pneumonia grouped terms (includes all PTs of pneumonia reported in this study), priapism, and osteonecrosis.

All AEs will be coded by primary system organ class (SOC) and preferred term (PT) according to the MedDRA Version 24.0 or higher and presented by participant in data listings.

The overall incidence of TEAEs (number of events, number and percentage of participants) will be summarized parts and overall. It includes: AEs, TEAEs, TEAEs by severity, SAEs, causally related TEAEs and SAEs, TEAEs leading to study or treatment discontinuation, life-threatening SAEs, and SAEs resulting in death.

The TEAEs will be summarized and tabulated at both the participant (n [%] of participants) and event (number of events) level:

- TEAEs by SOC and PT
- TEAEs by SOC, PT and maximum reported severity
- TEAEs by SOC, PT and closest relationship to study drug
- TEAEs by SOC, PT

For the incidence at the participant level by SOC and PT, if a participant experiences more than 1 event within the same SOC and PT, only 1 occurrence will be included in the incidence.

For the incidence at the participant level by SOC, PT, and severity, if a participant experiences more than 1 event within the same SOC and PT, only the most severe occurrence will be included in the incidence.

For the incidence at the participant level by SOC, PT, and relationship, if a participant experiences more than 1 event within the same SOC and PT, only the closest relationship will be included in the incidence.

Any SAEs, AEs with outcome of death, or AEs resulting in discontinuation of study or study drug will be listed separately.

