11.4. Safety Analysis

AEs will be coded to system organ class and preferred term using the Medical Dictionary for Regulatory Activities (MedDRA) and summarized. Vital signs and laboratory safety assessments will be presented with identification of values outside of normal range. Electrocardiogram data will be presented, with any clinically relevant abnormal findings or changes highlighted.

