4. CHANGES IN THE CONDUCT OF THE STUDY OR PLANNED ANALYSIS

All analyses specified in this SAP are consistent with the final study protocol (Version 6.0, Amendment 5 dated 08 March 2022). Any changes in this analysis provided or any additional analysis performed will be documented in CSR.

5. **QUALITY CONTROL AND QUALITY ASSURANCE METHODS FOR DATA ANALYSIS**

Case report forms will be monitored and processed according to the ICON Study Specific Procedure (SSP) DM-35070052.01 Data Management Plan (DMP). The DMP describes CRF data processing, edit checks, data query management, medical dictionary coding, SAE reconciliation, data transfers, and data quality review through database lock or any necessary reopening of the database. After database lock, the data will be retrieved from the database using SAS GRID Linux/SAS Studio - SAS® 9.4 version (or higher).

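### SAP 7.17.1 splits every adverse event summary into SCD-related and non-SCD-related sets without committing to a combined version, so followed literally it gives no combined count of participants with any TEAE, SAE or related TEAE

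*SAP*

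**What the plan says.** SAP 7.17.1 opens with a rule that covers every AE table: "All AE summaries will include treatment emergent AEs and will be presented for SCD related and SCD non-related separately".

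It then defines the SCD-related set by preferred term: "SCD-related AEs comprise the following PTs: sickle cell anemia with crisis, ACS, pneumonia grouped terms (includes all PTs of pneumonia reported in this study"), followed by priapism and osteonecrosis. Everything else is non-SCD-related.

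The section goes on to plan an overview: "The overall incidence of TEAEs (number of events, number and percentage of participants) will be summarized parts and overall". Its rows are named: "It includes: AEs, TEAEs, TEAEs by severity, SAEs, causally related TEAEs and SAEs, TEAEs leading to study or treatment discontinuation", together with life-threatening and fatal SAEs. After that come tables by SOC and PT, by maximum severity and by closest relationship to study drug. All AEs are listed by participant. SAEs, deaths and discontinuations also have separate listings.

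SAP 7.17 shows what overall means in the safety tables: "All safety data will be summarized by Part A (SAD), Part B (MAD) and Part C (extended treatment period) or overall (as applicable"). SAP 7.19 likewise says that safety tables are shown by part and overall.

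The primary objective (SAP 2.1.1, Protocol 4.1) is safety and tolerability. Protocol section 11 makes all analyses descriptive, with no formal tests.

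**The concern.** With no hypothesis test and a primary objective of safety and tolerability, the AE tables carry much of the main result. A reader of the study report will first want to know how many participants had any TEAE, any SAE or any TEAE judged related, and how severe the worst event was in each participant. The overview in 7.17.1 has rows for these counts, but the opening rule of the section would produce it twice, once for each set of preferred terms, and never combined.

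Participant counts from two such tables do not add up to the count for all events. A participant with a sickle cell crisis and a headache is counted once in each.

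**Working it through.** The documents state no figure to reproduce: the study has no formal sample size calculation, and the plan gives no AE counts. The check has two parts, a reading of the text and a bound on the lost information.

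**Reading the text**

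1. The opening rule of 7.17.1 applies to all AE summaries. The overview of TEAE incidence is an AE summary, so the rule covers it.
2. The overview is to be shown by parts and overall. In SAP 7.17 overall is the alternative to Part A, Part B and Part C, and SAP 7.19 pairs it with part in the same way. It therefore pools Parts. It does not say that SCD-related and non-SCD-related events are pooled.
3. No other sentence in the public SAP text exempts a table from the rule or promises a combined one.

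**Which counts are affected**

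- Each preferred term falls wholly in one set, so every PT row is complete. The rules in 7.17.1 for counting a participant once, at the worst severity or at the closest relationship, work within one SOC and PT and never cross the split.
- Each event has one preferred term, so event counts from the two sets add exactly.
- Participant counts that span preferred terms can cross the split. These are any TEAE, any SAE, any related TEAE, worst severity per participant, and SOC totals where a SOC holds both listed and unlisted terms.

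**Size of the gap**

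Inputs: N = 6 (SAP 3.5; the protocol says at least 6). Let a be the number of participants with an SCD-related event and b the number with a non-SCD-related event. The values of a and b below are illustrative.

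The number with any event lies between max(a, b), when the smaller group is contained in the larger, and min(N, a + b), when the two overlap as little as possible.

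| a | b | Lowest = max(a, b) | Highest = min(6, a + b) | Percent of 6 |
|---|---|---|---|---|
| 1 | 1 | 1 | 2 | 16.7 to 33.3 |
| 2 | 3 | 3 | 5 | 50.0 to 83.3 |
| 3 | 3 | 3 | 6 | 50.0 to 100 |
| 4 | 4 | 4 | 6 | 66.7 to 100 |
| 6 | 3 | 6 | 6 | 100 |

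The bounds coincide only if a or b is 0 or 6. With both between 1 and 5 the combined count is undetermined, which is 5 × 5 = 25 of the 7 × 7 = 49 possible pairs. The widest gap is 3 participants, at a = b = 3. The same bounds apply to SAEs, to related TEAEs and to participants at or above a given grade.

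**The case against.** The strongest reply is that the overview names exactly the rows in question, with numbers and percentages of participants, and that nothing says it lacks a combined column. SAP section 8 (the list of tables) and the AE shells are not in the public text, and the sentence in 7.19 on safety tables mentions no split. A combined table may exist there. This stands as a limit: the point concerns what the public SAP text commits to, not what the tables contain. It does not remove the point, because the only stated rule covers all AE summaries and points the other way.

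It is also fair that the harm is contained. PT rows and event counts are intact, and with about six participants the combined counts can be made by hand from the listings. But a hand count from a listing is not a planned summary.

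Three stronger readings are tempting, and the documents do not support them.

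- A reader might infer that the SAP conflicts with Protocol 11.4. That section says only: "AEs will be coded to system organ class and preferred term using the Medical Dictionary for Regulatory Activities (MedDRA) and summarized". It neither requires a single unsplit table nor forbids a split, so the SAP's statement in section 4 that "All analyses specified in this SAP are consistent with the final study protocol" is not contradicted on this ground.
- A reader might infer that a drug-related event with a listed term, such as a related pneumonia, is set aside as disease background. It is not. The relationship table is produced for both sets, and the event would appear as related in the SCD-related one. Nothing overrides the investigator's causality assessment, and there is no need to show the event twice.
- A reader might call the missing count the primary safety endpoint. The objective is safety and tolerability in general and names no single count.

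**Conclusion.** The point holds as a defect in the stated rule. Followed as written, SAP 7.17.1 yields no combined participant count for any TEAE, any SAE, any related TEAE or worst severity, and no combined SOC-level participant count. For 6 participants the uncertainty left by the two split counts is at most 3 participants (for example 3 to 6 of 6), and it is present for 25 of the 49 possible count pairs.

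This rests on three assumptions: that overall means across Parts, as SAP 7.17 and 7.19 indicate; that the unpublished list of tables and shells do not already provide combined tables; and that N is 6. The counts used are illustrative. The documents do not prove that the combined tables are missing, only that the public text does not plan them and its general rule would exclude them. The change is worth making because these counts serve the primary objective and cost almost nothing to add.

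**What to change.** Amend SAP 7.17.1 to say that the overall-incidence overview and the tables by SOC and PT, by maximum severity and by closest relationship are presented for all TEAEs combined, by Part and overall. Keep the SCD-related and non-SCD-related split as an additional presentation of the same tables. Make the list of tables match. If combined tables are already in the shells, only the opening sentence of 7.17.1 needs to change.

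If the SAP can no longer be amended, its section 4 allows an additional analysis to be documented in the CSR.

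The cost is a few extra tables from existing programs, with no new data and no new derivations. The bullet list in 7.17.1 names the SOC/PT table twice, so it needs an edit in any case.
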